Anti HBs and anti HBe	X		X							X								X	
HBsAg (qualitative)	X																	X	
HBeAg (qualitative) dd	X									X								X X	
HBsAg (quantitative)	X		X	X	X	X	X	X	X	X	X	X	X	X			X X		
HBeAg (quantitative) ee			X	(X)	(X)	(X)				(X)								(X)	
HBcrAg bb	X		X		X		X			X		X		X			X X		
Exploratory serology ff	X		X	X	X	X	X	X	X	X	X	X	X	X			X X		
Clinical Pharmacology Assessments																			
Blood sampling for sparse PK of JNJ 3989, and NA gg			X hh		X hh		X hh		X hh									X ii	
Blood sampling for intensive PK of JNJ 3989, and NA (PK substudy) jj					X														
Exploratory Host Biomarkers																			
Whole blood RNA gene expression			X	X			X			X				X				X	
Whole blood single cell profiling	X	X	X	X	X	X				X		X	X	X				X	
Host serum proteins (eg, cytokines)			X		X	X	X			X		X	X					X	
Antidrug antibodies (to JNJ 3989)			X							X								X	
Immune Monitoring																			
Leukapheresis (optional) kk			(X)															(X)	
Immune cells (PBMCs) ll	X									X			X						
Pharmacogenomics (Host DNA)																			
HLA typing			X																
Exploratory host genotyping mm			X																
Epigenetic research			X							X			X					X	
Ongoing Participant Review																			
Concomitant therapy nn	X	X	X	X	X	X	X	X	X	X	X	X	X	X	X	X	X X		
Adverse events nn,oo	X	X	X	X	X	X	X	X	X	X	X	X	X	X	X	X	X X		

ALP: alkaline phosphatase; ALT: alanine aminotransferase; AST: aspartate aminotransferase; CKD-EPI: Chronic Kidney Disease Epidemiology Collaboration; CRF: case report form; CT: computed tomography; D/d: day; DBP: diastolic blood pressure; DNA: deoxyribonucleic acid; ECG: electrocardiogram; eGFR: estimated glomerular filtration rate; FSH: follicle-stimulating hormone; HBc: hepatitis B core protein; HBe(Ag): hepatitis B e (antigen); HBcrAg: hepatitis B core-related antigen; HBs(Ag): hepatitis B surface (antigen); HBV: hepatitis B virus; HCC hepatocellular carcinoma; HIV-1 (-2): human immunodeficiency virus type 1 (type 2); HLA: human leukocyte antigen; ICF: informed consent form; IgM: immunoglobulin M; MRI: magnetic resonance imaging; NA: nucleos(t)ide analog; PBMC: peripheral blood mononuclear cell; PK: pharmacokinetic; RNA: ribonucleic acid; SBP: systolic blood pressure; ULN: upper limit of normal; W/w: week; WD: withdrawal.

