- x. Urine chemistry sample (quantitative measurement): creatinine, sodium, phosphate, glucose, protein, and albumin.
- y. Urine sample for selected renal biomarkers including retinol binding protein and beta-2-microglobulin.
- z. For postmenopausal women only: an FSH level in the postmenopausal range may be used to confirm a postmenopausal state in women not using hormonal contraception or hormonal replacement therapy. However, in the absence of 12 months of amenorrhea, a single FSH measurement is insufficient to confirm a woman is not of childbearing potential.
- aa. HBV genotype will be determined at baseline using standard genotyping assay if HBV DNA levels are sufficiently high. For participants with low HBV DNA levels, available historical data on previous HBV genotype assessment will be collected in the CRF. Exploratory genotyping assays might be performed.
- bb. HBcrAg and HBV RNA samples may be batched and only selected samples may be tested at the sponsor's request. Samples can be used for assessment of other serologic/virologic markers of HBV.
- cc. Samples may be sequenced based on the sponsor virologist's request, considering the HBV DNA levels.
- dd. Participants must first complete HBeAg testing and have results reviewed by the investigator to confirm if they qualify for study participation.
- ee. Quantitative HBeAg assessment will only be performed in participants who are defined HBeAg positive at screening or who become HBeAg positive post-baseline based on a qualitative HBeAg assay.
- ff. Exploratory serology samples may be analyzed at the sponsor's discretion. Samples may be used to assess virologic or serologic markers of HBV.
- gg. All participants will have sparse PK sampling for JNJ-3976, JNJ-3924, and NA (ETV, TAF, or tenofovir). Bioanalysis of NA and/or PegIFN- $\alpha$ 2a is optional at the discretion of the sponsor. Bioanalysis of JNJ-6379 may also be done on samples collected from participants who received JNJ-6379 up to Protocol Amendment 4. For all samples, the date and time of the preceding intake of oral study intervention (NA), the date and time of the previous JNJ-3989 administration, and the date and time of PK sampling should be recorded. Sparse PK sampling is not required if the participant is part of the intensive PK subgroup and has an extensive PK sampling at the same visit.

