### 1.3.3. Schedule of Activities – Optional PegIFN- $\alpha$ 2a Treatment

Participants who provide separate consent, may receive treatment with optional PegIFN- $\alpha$ 2a starting after the Week 40 biopsy (or after the optional leukapheresis if applicable) but before the Week 48 visit. The duration (either 12 or 24 weeks) will be at the investigator's discretion.

**In addition to the main schedules of activities (refer to Sections 1.3.1 and 1.3.2), the following visits and assessments will be performed for participants receiving PegIFN- $\alpha$ 2a.**

Phase		Optional PegIFN $\alpha$ 2a treatment				Comments
Additional visits	Before	Start	+2 wks	+4 wks	End (+12 or 24 wks)	
Study Day (relative to start of PegIFN $\alpha$ 2a treatment)		1	15	29	85 or 169	
ICF for PegIFN $\alpha$ 2a treatment	X					Participants must sign a separate ICF prior to the start of PegIFN <math>\alpha</math>2a treatment. Refusal to give consent for this optional treatment does not exclude a participant from participation in the study.
Exclusion criteria for PegIFN $\alpha$ 2a treatment	X					To be checked prior to the start of PegIFN <math>\alpha</math>2a treatment (refer to Section 5.2).
Administer PegIFN $\alpha$ 2a for 12 or 24 weeks		(Weekly)				All PegIFN <math>\alpha</math>2a administrations (on study visits and in between study visits) should preferably be done in the evening by self injection. If desired, participants can also choose to have the weekly administration of PegIFN <math>\alpha</math>2a performed on site irrespective of the time of day.
Dispense PegIFN $\alpha$ 2a		(Every 4 weeks)				Participants will receive PegIFN <math>\alpha</math>2a supply for self administration at home in between study visits.
Study intervention accountability			X	X	X	
Body weight and Symptom directed physical examination		X	X	X	X	
Ophthalmic examination	X	(As applicable)				Periodic ophthalmologic examinations during PegIFN <math>\alpha</math>2a treatment are at the investigator's discretion. Any patient who develops ocular symptoms should receive a prompt and complete eye examination.
Injection site reactions for PegIFN $\alpha$ 2a		(At every visit)				
Hematology			X	X		
Blood chemistry (including liver function tests)				X		
Blood sampling for HBV DNA		X			X	
Blood sampling for HBsAg (quantitative)		X			X	
Blood sampling for HBeAg (quantitative)		X			X	

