5.4.2.3. HBeAg Seroclearance and Seroconversion

Seroclearance of HBeAg is defined as (quantitative) HBeAg <LLOQ. The HBeAg seroclearance will be summarized only for HBeAg positive participants at study entry.

Seroclearance will be analyzed as observed case without imputation and with imputation using LOCF approach. For the imputation with LOCF approach, we impute the missing data with the following restriction. If the HBeAg value at Weeks 40 or 48 is missing, the LOCF approach will be used with the condition that no value more than 8 weeks prior to the respective time point may be carried forward. At FU Weeks, if an HBeAg value is missing, then LOCF approach will be used

with the condition that no value before the FU phase or more than 12 weeks prior to the respective time point will be used. For all other time points, seroclearance will be analyzed as observed case without imputation.

The proportion of participants who achieve HBeAg seroclearance over time will be summarized.

Seroconversion of HBeAg is defined as having achieved HBeAg seroclearance together with appearance of anti-HBe antibodies. Appearance of anti-HBe antibodies is defined as a baseline anti-HBe antibodies (qualitative) with a "NEGATIVE" result and a post-baseline assessment with "POSITIVE" result. The seroconversion of HBeAg will be summarized only for HBeAg positive participants at study entry.

The seroconversion will only be assessed at the time points when the anti-HBe antibodies assessment is available. If the HBeAg value is missing at that specific time point, then the non-missing lab test closest to that specific timepoint will be used. If the non-missing lab test before and after the specific timepoint fall equidistant from the target timepoint, the later one will be used to impute the missing value.

The number and proportion of participants who achieve HBeAg seroconversion will be summarized.

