5.5. Exploratory Endpoints Analysis

5.5.1. Relationship Between Intrahepatic and Blood Markers

Relationships between intrahepatic and blood markers (Table 4) and/or their change from baseline at Week 40 will be evaluated graphically with scatter plots displaying individual associations.

Means on pooled individual data by study panel and overall mean will also be plotted on the same graph.

The following correlation coefficients will be calculated by study panel and overall for the different correlation scenarios:

- Pearson's correlation coefficient for two continuous variables.
- Phi correlation coefficient for two binary variables.
- Point biserial correlation coefficient for one binary variable and one continuous variable.

Potential relationship on the selected subgroups defined in Section 5.7.4 will also be explored using the same graphical approach.

The following markers will be considered, i.e., each intrahepatic marker will be plotted against each blood marker:

Table 4: List of Intrahepatic and Blood Markers of Interest

Intrahepatic Markers/Endpoints	Blood Markers/Endpoints
• Proportion of HBsAg+ hepatocytes at Week 40	• HBV DNA level at Week 40 (\log_{10})
• Change from Baseline at Week 40 in proportion of HBsAg+ hepatocytes	• HBV RNA level at Week 40 (\log_{10}) • HBsAg level at Week 40 (\log_{10})

 • Proportion of cccDNA-positive hepatocytes at Week 40 • Change from Baseline at Week 40 in proportion of cccDNA-positive hepatocytes • Proportion of pgRNA-positive hepatocytes at Week 40 • Change from Baseline at Week 40 in proportion of pgRNA-positive hepatocytes • pgRNA levels at Week 40 (\log_{10} copies/ cell) • Change from Baseline at Week 40 in pgRNA levels (\log_{10} copies/ cell) • 	
 • HBeAg level at Week 40 (\log_{10}) • HBcrAg level at Week 40 (\log_{10}) • Change from Baseline at Week 40 in HBV DNA (\log_{10}) • Change from Baseline at Week 40 in HBV RNA (\log_{10}) • Change from Baseline at Week 40 in HBsAg (\log_{10}) • Change from Baseline at Week 40 in HBeAg (\log_{10}) • Change from Baseline at Week 40 in HBcrAg (\log_{10}) • Maximum on-treatment ALT decrease • HBsAg seroclearance at FU Week 24
--	---

Additional markers and endpoints may be evaluated when data will be available.

5.5.2. Association Between Baseline Characteristics or Intrahepatic/Blood Markers with Efficacy Variables

The following list of efficacy endpoints of interest will be evaluated:

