- Proportion of participants with HBsAg <10 IU/mL at Week 40 (Yes/No)
- Proportion of participants with HBsAg <10 IU/ml at Off-Treatment Week 24 (Yes/No)
- Proportion of participants with HBsAg Seroconversion at Off-Treatment Week 24 (Yes/No)
- Proportion of participants with Functional Cure at Off-Treatment Week 24 (Yes/No)

For each of the endpoints listed above, the potential association with the following selection of characteristics or intrahepatic/blood markers may be assessed:

- Duration of NA (years)
- Age (years)
- Duration of infection (years)
- Baseline HBeAg level (quantitative), for panel 1 only
- Baseline HBV DNA level (\log_{10})
- Baseline ALT Level (quantitative)
- Baseline Peripheral HBsAg level (\log_{10})
- Baseline Number of HBsAg+ hepatocytes (\log_{10})
- Proportion of HBsAg+ hepatocytes at baseline
- Proportion of cccDNA-positive hepatocytes at Baseline
- Proportion of pgRNA-positive hepatocytes at Baseline
- HBeAg level (quantitative) at Week 40

- HBV DNA level (\log_{10}) at Week 40
- ALT Level (quantitative) at Week 40
- Peripheral HBsAg level (\log_{10}) at Week 40
- Proportion of HBsAg+ hepatocytes (\log_{10}) at Week 40
- Proportion of cccDNA-positive hepatocytes at Week 40
- Proportion of pgRNA-positive hepatocytes at Week 40

These lists may be modified based on clinical relevance and data availability.

For Panels 1 and 2, logistic regression models will be performed for each efficacy endpoint of interest, and will include study panel and characteristics/marker of interest as factor, with and without the study panel-by-baseline variable as the interaction-terms. Covariates and/or interaction terms may be added or removed to a given model for fitting purpose.

Odd-Ratios (OR) and corresponding 80% CIs will be also calculated without multiplicity adjustment overall. Statistical analysis of treatment heterogeneity between subgroups will be conducted by assessing the significance of the interaction term. The forest plot will present graphically the on/off treatment efficacy OR estimate and its 80% CI resulting from the model by the prespecified subgroups on the overall population and by study panels.

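### The SAP analyses HBeAg at Week 40 in three places, but the protocol schedules no HBeAg sample at that visit

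*SAP*

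**What the plan says.** The SAP uses HBeAg at Week 40 in three places.

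- **Section 5.5.1, Table 4.** The blood markers include HBeAg level at Week 40 and "Change from Baseline at Week 40 in HBeAg", both on the log10 scale. Each intrahepatic marker is to be plotted against each blood marker, and correlation coefficients are to be calculated by panel and overall.
- **Section 5.5.2.** The markers that may be related to the efficacy endpoints by logistic regression include "HBeAg level (quantitative) at Week 40".
- **Section 5.4.2.3**, a secondary-endpoint section. Seroclearance is defined on quantitative HBeAg, restricted to participants HBeAg positive at study entry, and summarised over time. The section says "If the HBeAg value at Weeks 40 or 48 is missing, the LOCF approach will be used", with no value older than 8 weeks carried forward.

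In protocol section 1.3.1, the row "HBeAg (quantitative) ee" has marks at Day 1, three early visits, about Week 24, and an end-of-intervention cell. The row "HBeAg (qualitative) dd" has marks at screening, about Week 24, and Weeks 44 and 48. Neither has a mark at Week 40. Footnote ee adds "Quantitative HBeAg assessment will only be performed in participants who are defined HBeAg positive at screening" or who become positive later, so the marker concerns mainly Panel 1. Section 1.3.3 adds "Blood sampling for HBeAg (quantitative" at the start and end of PegIFN-α2a, for participants who opt for that treatment.

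**The concern.** Week 40 is the on-treatment biopsy and the time point of the primary endpoint, and HBeAg positivity defines Panel 1. The plan asks how HBeAg and its change from baseline relate to liver tissue at that visit, but the schedule supplies no such value for Panel 1 as a whole.

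A programmer who follows the SAP literally will get either empty cells or results from the few participants who happen to have a draw inside the window. The second outcome is the worse one. The output would look like a Week 40 result for HBeAg-positive participants, while resting on those who chose PegIFN and started it early, or on those who stopped treatment early.

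**Working it through.** No sample size or error rate is involved. The check compares the schedule with the SAP's time windows.

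**Inputs**
- Week 40 analysis window: Days 268 to 295, target Day 281 (SAP Table 2).
- Visit target days: Week 24 = 169, Week 44 = 309, Week 48 = 337, each ±3 days (protocol 1.3.1).
- Week 40 biopsy: Day 281 ± 4 weeks (protocol 1.3.1).
- PegIFN start: after the Week 40 biopsy, or after the optional leukapheresis (1 to 3 weeks after the biopsy), and before Week 48 (protocol 1.3.3; 1.3.1 footnote kk).
- Carry-forward limit at Week 40: 8 weeks (SAP 5.4.2.3).

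**Step 1. Is the Week 40 cell empty?** Counting cells against the 19 visit columns, both HBeAg rows are blank at Week 40. Control rows in the same table (quantitative HBsAg, HBcrAg, viral sequencing, exploratory serology) all carry a Week 40 mark.

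**Step 2. Does a scheduled HBeAg visit reach Days 268 to 295?**
- Week 24: 166 to 172, no.
- Week 44: 306 to 312, no.
- Week 48: 334 to 340, no.

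The last columns of the table are merged, so the final quantitative mark could be Week 44 or Week 48. Neither overlaps.

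**Step 3. Can carry-forward fill it?** Earliest admissible day = 281 − 8 × 7 = 225. The Week 24 target gives a gap of (281 − 169)/7 = 16 weeks, twice the limit. If the Week 24 mark were misplaced by one column and really stood at Week 28 (Day 197), the gap would be (281 − 197)/7 = 12 weeks, still too long. The rule is also written only for seroclearance, so it does nothing for Table 4 or 5.5.2. The nearest-value rule for HBeAg seroconversion does not help either: it applies only where anti-HBe is available, and anti-HBe has no Week 40 mark.

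**Step 4. Which planned draws can fall in the window?**
- *PegIFN start sample.* It must be taken by Day 295.
  - Biopsy on Day 281: starts on Days 282 to 295 qualify, or Days 288 to 295 if leukapheresis comes first.
  - Biopsy on Day 294: only Day 295 qualifies, and only without leukapheresis.
  - Biopsy between Day 295 and the upper limit of Day 309 (281 + 28): none qualifies.
- *Early-withdrawal visit.* The Week 48 column doubles as the withdrawal visit, so a withdrawal in Days 268 to 295 could supply a value.

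**Step 5. How much is affected?** Table 4 has ten Week 40 blood entries (five levels and five changes), and two of them are HBeAg. With eight intrahepatic entries and twelve blood entries in all, this touches 8 × 2 = 16 of 8 × 12 = 96 pairings. Add one candidate predictor in 5.5.2 and one time point of the seroclearance summary. The number of Panel 1 participants with a scheduled Week 40 HBeAg is 0 of about 12.

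**The case against.** The best defence is that the data may exist although the schedule does not ask for them. Exploratory serology is drawn at Week 40, and footnote ff says "Exploratory serology samples may be analyzed at the sponsor's discretion. Samples may be used to assess virologic or serologic markers of HBV". Footnote bb gives a similar permission for the HBcrAg and HBV RNA samples. SAP Amendment 2 revised the 5.5.2 list to match the data actually collected, and Week 40 HBeAg stayed in. This stands to the extent that a reader might infer from the schedule that the Week 40 HBeAg results must be empty or can come only from PegIFN starters. The documents do not support that: discretionary testing cannot be ruled out, and an early withdrawal could also contribute. But neither document plans the test, and the amendment log describes that revision in terms of intrahepatic markers.

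A second defence is flexibility. The 5.5.2 lists may be modified for data availability, and an exploratory plot without data can simply be omitted. That clause covers the 5.5.2 lists only; 5.4.2.3 has no equivalent. It also gives no protection against a plot built on a handful of selected values.

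Third, the schedule was read from a damaged table. The sparse PK row, counted in the same way, puts a mark at Week 20 where the text says Week 24. That is a one-column error. Moving the final quantitative HBeAg mark to Week 40 would take about four columns.

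A reader might also infer that HBeAg cannot be paired with liver tissue at all. That goes too far. Day 1 HBeAg pairs with the Week −1 biopsy, and a late Week 40 biopsy can reach Day 309, the Week 44 visit, where qualitative HBeAg is drawn. That draw still does not supply the planned variable: the SAP assigns it to Week 44, and both the seroclearance definition and the levels need the quantitative assay.

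**Conclusion.** The mismatch holds. The protocol schedules no HBeAg sample at Week 40, the SAP plans three uses of one, and no SAP rule bridges the 16 weeks from the last scheduled value. As written, the plan yields no Week 40 HBeAg result, or one from a selected few, unless stored serum is tested at the sponsor's discretion.

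The consequence is limited. Table 4 and 5.5.2 are exploratory, no hypothesis is tested, and only one time point of a secondary summary is affected. HBeAg seroclearance at Week 48 is still planned. The primary endpoint does not use HBeAg, and the laboratory check for completing NA treatment uses Week 44, where HBeAg is scheduled. The size of any selection bias cannot be stated, because the documents give no figure for PegIFN uptake or start dates.

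The conclusion assumes that the extracted table is right to within a column or so. It covers Panels 1 and 2 only; the country-specific schedule for Panel 3 is not among the documents.

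**What to change.** **Preferred.** If residual serum allows, run quantitative HBeAg on the Week 40 exploratory serology sample already collected from participants HBeAg positive at study entry, and state in the SAP that this is the source. The cost is about 12 assays for Panel 1, with no new visit or draw. Volume and stability of the stored serum are not given in the documents and must be confirmed first. Adding a Week 40 mark to the schedule would help only participants who have not yet reached that visit.

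**Otherwise.** Remove the Week 40 HBeAg entries from Table 4, 5.5.2 and 5.4.2.3. State that Week 40 HBeAg summaries or correlations will not be reported if they rest only on PegIFN start or early-withdrawal samples. This is a wording change.

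**If Week 48 HBeAg is substituted in Table 4 or 5.5.2**, label it as about 8 weeks after the target biopsy date (337 − 281 = 56 days) and as measured after PegIFN start in those who opted in. Without that label, the substitute mixes PegIFN exposure into a comparison with tissue taken before it.

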## 4. STUDY DESIGN

### 4.1. Overall Design

As of Protocol Amendment 5, the study is a Phase 2 single-arm, open-label, multicenter, study to assess intrahepatic and peripheral changes of immunologic and virologic markers in response to a combination regimen containing JNJ-3989 and NA in chronic HBV-infected participants.

With the implementation of an urgent safety measure, as described in Protocol Amendment 5, JNJ-6379 has been removed as study intervention and the study will continue as a single-arm study. Participants randomized to Arm 1 had to stop JNJ-6379 treatment immediately but continue JNJ-3989 + NA treatment.

In addition, participants who provide separate consent may receive optional treatment with PegIFN- $\alpha$ 2a starting after the Week 40 biopsy (or after the optional leukapheresis if applicable) but before the Week 48 visit. The duration (either 12 or 24 weeks) will be at the investigator's discretion.

A target of 24 chronic HBV-infected male and female participants, 18-65 years (inclusive) of age will be enrolled in 2 panels, approximately 12 participants in each panel. Panel 1 will consist of participants who are HBeAg positive and not currently treated and Panel 2 will consist of participants who are HBeAg negative and virologically suppressed by ETV, tenofovir disoproxil, or TAF treatment.

The study will be conducted in 3 phases for all participants: a screening phase (4 weeks), an open-label study intervention phase (48 weeks), and a follow-up phase (48 weeks). If necessary, eg, for operational reasons, the screening phase may be extended up to a maximum of 6 weeks on a case-by-case basis and in agreement with the sponsor. The duration of individual participation will be up to 102 weeks. Note that the follow-up period will be extended for participants who are receiving optional treatment with PegIFN- $\alpha$ 2a and who meet NA treatment completion criteria at the end of

treatment with NA and PegIFN- $\alpha$ 2a to ensure all participants have at least one year of follow-up after NA treatment cessation. For those participants, the duration of individual participation may be extended up to 126 weeks.

Prior to Protocol Amendment 5, participants were randomized in a 1:1 ratio within each panel to receive one of the following interventions (ie, treatments) for 48 weeks:

- Intervention arm 1, combination regimen JNJ-3989+JNJ-6379+NA (target of 12 participants):  

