### **9.4. Statistical Analyses**

The Statistical Analysis Plan will include a more technical and detailed description of the statistical analyses described in this section. This section is a summary of the planned statistical analyses of the most important endpoints including primary and key secondary endpoints.

Given the exploratory nature of the study and the limited sample size per panel, no statistical testing will be performed. All data will be summarized descriptively including 80% confidence intervals as appropriate.

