#### Amendment 4 (30 July 2021)

**Overall Rationale for the Amendment:** The primary reason for this amendment is to offer participants optional treatment with PegIFN- $\alpha$ 2a for either 12 or 24 weeks starting after the Week 40 biopsy (or after the optional leukapheresis if applicable), to investigate whether addition of PegIFN- $\alpha$ 2a towards the end of the treatment regimen may enhance response to treatment. This change is based on the availability of preliminary 48-week treatment data from the Phase 2b study REEF-1 (73763989HPB2001) and new data presented during the European Association for the Study of the Liver (EASL) conference of 2021 showing that HBsAg declines with siRNA treatment can be increased when combined with PegIFN.

The REEF-1 study is evaluating the efficacy of 3 doses of JNJ-3989 (40, 100, or 200 mg Q4W) + NA, of JNJ-3989 100 mg Q4W + JNJ-6379 + NA, of JNJ-6379 + NA, and of NA alone. Data showed that all regimens were safe and well-tolerated through end of treatment at Week 48. The JNJ-3989 200 mg dose achieved the highest response rate (19.1%) for the primary endpoint of meeting the NA treatment completion criteria at Week 48 (ie, ALT <3x ULN, HBV DNA <LLOQ, HBeAg-negative [<LLOQ], and HBsAg <10 IU/mL). No participant in the JNJ-6379 + NA arm and 1 participant in the NA alone arm achieved the primary endpoint. The largest mean (SD) decline at Week 48 of 3.56 (1.328) log10 IU/mL was observed in the JNJ-3989 200 mg + NA arm in the HBeAg positive currently not treated participants. The mean HBsAg decline followed a biphasic pattern, with a steeper decline during the first 24 weeks followed by a more shallow decline between Week 24 and Week 48. At Week 48, a limited number of participants reached HBsAg seroclearance.

This amendment will allow to investigate whether addition of PegIFN- $\alpha$ 2a for 12 or 24 weeks at or after the Week 40 biopsy increases the participant's chances to achieve HBsAg loss.

Description of Change	Brief Rationale	Section Number and Name

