5.1.7. Level of Significance

Due to the exploratory nature of this study, no formal statistical test will be performed. Two-sided 80% CI will be provided with the summary statistics. No adjustment for multiple CIs will be made.

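### SAP 5.5.2 assesses the significance of treatment heterogeneity, which the plan rules out elsewhere and the model cannot estimate, and it has no rule for sparse events

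*SAP*

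**What the plan says.** SAP 5.5.2 lists four binary endpoints: HBsAg <10 IU/mL at Week 40, and HBsAg <10 IU/mL, HBsAg seroconversion and functional cure at Off-Treatment Week 24. It lists 18 candidate characteristics or markers. For Panels 1 and 2, "logistic regression models will be performed for each efficacy endpoint of interest", and these models "will include study panel and characteristics/marker of interest as factor, with and without the study panel-by-baseline variable as the interaction-terms". Odds ratios with 80% CIs follow, without multiplicity adjustment. Terms may be added or removed to help the fit. Then: "Statistical analysis of treatment heterogeneity between subgroups will be conducted by assessing the significance of the interaction term".

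SAP 5.1.7 says: "Due to the exploratory nature of this study, no formal statistical test will be performed". Protocol 9.4 says: "Given the exploratory nature of the study and the limited sample size per panel, no statistical testing will be performed". Protocol 4.1 states that, as of Amendment 5, "the study is a Phase 2 single-arm, open-label, multicenter, study". The note under Figure 2 in SAP 1.2 adds that former Arm 1 participants are analysed with Arm 2. SAP Appendix 2 declares no departure from the protocol-planned analyses.

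**The concern.** There are two separate problems.

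First, a significance assessment is planned in a study that says it will test nothing, at no stated level, and it is attached to a term that does not measure what it is called. Panels 1 and 2 differ in HBeAg status and in NA treatment at entry, and both receive the same regimen. A panel-by-marker interaction describes a difference between those populations. Reported under the planned label, it invites the wrong reading.

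Second, the models may have very few events. The SAP names no small-sample estimator, no minimum event count, and no trigger for dropping a term. Odds ratios in the forest plots could then be infinite or span orders of magnitude, and the choice of model would be made after seeing which fits behave.

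**Working it through.** **The plan's own figures.** Section 5.5.2 gives no sample size, event count or level for these models. The only precision figures concern the primary endpoint. SAP Section 3 gives 80% CI widths of 16.7%, 17.9% and 20.3% for N = 24, 20 and 16. A large-count approximation to the SAP's binomial mixed model gives 16.5%, 18.2% and 20.2%, so those reproduce. With 20% dropout, 12 x 0.8 = 9.6 per panel, matching the 9-10 in Attachment 1. None of this bears on a rare binary endpoint.

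**Testing and label.** Setting the sections side by side is enough. SAP 5.1.7 and Protocol 9.4 allow no test; SAP 5.5.2 assesses significance. The model terms are panel, marker and their product. No term codes treatment.

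**Event counts.** Neither document gives a rate for the four endpoints. The nearest figure is in the Amendment 4 rationale (Protocol 10.10): 19.1% met the NA completion criteria at Week 48 on the 200 mg dose in the Phase 2b study REEF-1. Carrying it over is an assumption. I use N = 24 throughout.

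- Expected events: 24 x 0.191 = 4.6; with 20% dropout, 4.6 x 0.8 = 3.7.
- Probability of five or fewer events (binomial): 0.70.
- Probability that at least one panel has no event: 1 - (1 - 0.809^12)^2 = 0.15.
- Events per slope: 4.6/2 = 2.3 for panel + marker; 4.6/3 = 1.5 with the interaction.

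**Finite fits.** Simulation with 12 per panel, a standard-normal marker, true odds ratio 1 or 3 per SD, no true interaction and 800 runs per setting. Each fit was checked for complete or quasi-complete separation. The ranges span the two odds ratios.

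| Assumed rate | Events of 24 | No finite ML fit: panel + marker | No finite ML fit: with interaction |
|---|---|---|---|
| 5% | 1.2 | 78-80% | 85-88% |
| 10% | 2.4 | 50-51% | 59-68% |
| 19.1% | 4.6 | 15-17% | 26-35% |
| 30% | 7.2 | 2-3% | 6-17% |
| 40% | 9.6 | about 1% | 2-12% |

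At 19.1%, when the interaction fit was finite, the median ratio of upper to lower 80% limit for its odds ratio was about 42 to 139. At 30-40% it was still 18 to 83.

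**Penalised fits.** Firth fits at N = 24 and 19.1% converged in every run with at least one event. The median 80% limit ratio was about 4-6 for the marker in the panel + marker model and 25-45 for the interaction. Penalisation cures non-convergence but leaves the interaction uninformative.

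**Failures by construction.** HBsAg <10 IU/mL at Week 40 is a cut of the Week 40 HBsAg level. If both outcomes occur, that predictor separates them completely. Baseline HBeAg is listed for Panel 1 only, so panel is constant and neither the panel term nor the interaction can be estimated.

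**Multiplicity.** The full menu is 4 x 18 = 72 pairs. Under no effect, 72 x 0.20 = 14.4 nominal positives at the level implied by 80% CIs, or 72 x 0.05 = 3.6 at 5%.

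**The case against.** The section is exploratory and permissive: associations may be assessed, the lists may be modified, and terms may be removed. A panel + marker model is already one of the two planned. This stands, and it means 72 is a ceiling on the pairs, with no commitment to run them all. It does not supply a rule, because the SAP gives no trigger, minimum count or fallback estimator.

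A reader might infer that every model will have about five events or fewer. The documents do not support that. The 19.1% is a Week 48 composite that also requires ALT, HBV DNA and HBeAg criteria. At any one visit, HBsAg <10 IU/mL alone is met at least as often as the composite, so the Week 40 endpoint could have 7 to 10 events. For the off-treatment endpoints, 4.6 is plausible because they depend mainly on having stopped NA. It is not a firm cap, since NA may also be stopped later, at the end of PegIFN treatment.

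A reader might also infer that these models will separate and give infinite odds ratios. At 19.1% most fits are finite, though unstable. Failure in most runs needs rates nearer 5-10%. That the estimator is ordinary maximum likelihood is itself inferred from the SAP naming no other method.

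It could be said that treatment means PegIFN use, which is a subgroup in SAP 5.7.4. But Section 5.5.2 defines the interaction as panel by baseline variable, and PegIFN is not in that model.

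**Conclusion.** The wording defect is established from the documents alone. The sentence contradicts the no-testing statements, sets no level, and calls a panel-by-marker term treatment heterogeneity when the model has no treatment contrast. The two combinations that fail by construction are equally certain.

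The sparse-event problem is likely, but its size rests on assumptions: a rate borrowed from another study, equal rates in both panels, and N = 24. Over 5-40% the expected count runs from 1.2 to 9.6, and the share of interaction models with no finite fit runs from 85-88% down to 2-12%. Even where fits are finite, the interaction carries almost no information at this sample size.

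Two further inferences go too far. The 14 or so nominal false positives are not a forecast: at 19.1%, finite fits rejected in only about 8-16% of runs at the 20% level. Nor do the documents show that panel differences will be reported as treatment effects; the label only makes that easier.

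**What to change.** - Delete the significance sentence. Call any such term an exploratory panel-by-marker interaction and report it with an 80% CI only.
- Name the estimator: Firth-penalised (or exact) logistic regression with panel and marker as the default model.
- State a minimum event count below which the interaction is omitted, and a lower one below which only descriptive plots are shown. Set both before the final endpoint counts are known. The working suggests the interaction threshold should lie above 7 to 10 events, where the interval is still very wide.
- Drop Week 40 HBsAg level as a predictor of HBsAg <10 IU/mL at Week 40. Firth would return a finite but meaningless odds ratio for it.
- Fit baseline HBeAg within Panel 1, without a panel term.

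The cost is SAP wording and one model option, with no new data. Penalised estimates are shrunk toward the null, and fewer interaction results will be shown.
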